**Does Low Flow Anesthesia Affect Cerebral Oxygenization in Bariatric Surgery?
Prospective Randomized Clinical Study**

[name], Asst. [name] of Anesthesiology and Reanimation, Inonu University Medical Faculty, Malatya, Turkey

[name], Asst. [name] of Anesthesiology and Reanimation, Inonu University Medical Faculty, Malatya, Turkey

Address all correspondence to:

[name], Asst. [name] of Anesthesiology and Reanimation, Inonu University Medical Faculty, Malatya, Turkey

Mail: [contact]

[contact]

Keywords: Bariatric surgery, low flow anesthesia, bispectral index, regional cerebral oxymetry

Does Low Flow Anesthesia Affect Cerebral Oxygenization in Bariatric Surgery? Prospective Randomized Clinical Study

Study Protocol

This study will perform in 60 adult patients who undergoing laparoscopic sleeve gastrectomy or gastric bypass surgery. Morbidly obese patients with ASA (American Society of Anesthesiology) score I-III, aged 18-65 years, BMI > 35 will include in the study. Patients with ASA IV, under 18 years, over 65 years, obstetric patients, uncontrolled diabetes mellitus, cardiovascular and pulmonary disease, cerebrovascular disease and patients who refused informed consent forms will exclude from the study.

Heart rate (HR), noninvasive blood pressure, electrocardiogram (ECG) and peripheral oxygen saturation (SpO₂), monitoring will perform to all patients in operation room without premedication. In addition, regional cerebral oxygen saturation (Near-infrared spectroscopy system, NIRS, INVOS 4100 Cerebral Oximeter, Software Version 7.2.5.0, Somanetics Corporation) and BIS (Bispectral Index, VISTA™ Monitoring System) monitoring will perform to all patients. Two cerebral sensors of NIRS and BIS sensors will glue to the right and left frontal areas under the hairline and covered with tape to prevent exposure to light.

After preoxygenation (100% 4 L/min O₂ for 3 minutes), propofol (1-2 mg/kg), rocuronium (0.8 mg/kg) and fentanyl (0.1 µg/kg) will administer in anesthesia induction via intravenous route at doses calculated according to ideal body weights. Randomly select patients will divide into two groups: Group L: low flow desflurane and group N: normal flow desflurane. Initially, anesthesia maintain with desflurane inhalation with a flow of 2 L/min in 0.5 O₂ oxygen-air mixture in both groups. While target minimum alveolar concentration (MAC) was 1-1.5 and BIS values are 40-60 concurrently, the flow rate adjust to 0.75 L/min in Group L and 1.5 L/min in Group N. Age-related MAC values will determine and express as a percentage of volume. The ventilation parameters will adjust to maintain the end-tidal carbon dioxide (EtCO₂) values at 35-45 mmHg. Neuromuscular blocker will administer based on Train of Four (TOF, Datex-Ohmeda) values.

HR, SpO₂, EtCO₂, mean arterial pressure (MAP), BIS values, left regional cerebral oxygen saturations (LrSO₂) and right regional cerebral oxygen saturations (RrSO₂) will record at before anesthesia (T₀), after intubation (T₁), before insufflation of CO₂ (T₂), after insufflation of CO₂ (T₃), after reverse trendelenburg position (T₄), after supine position (T₅), after desufflation of CO₂ (T₆), after awakening from anesthesia (T₇). Also anesthesia and surgery times, perioperative and postoperative complications will record. Postoperative analgesia was achieved in all patients with appropriate doses of tramadol and paracetamol via intravenous route.

Does Low Flow Anesthesia Affect Cerebral Oxygenization in Bariatric Surgery? Prospective Randomized Clinical Study

Statistical Analysis

Statistical analysis will carry out by using SPSS program (SPSS for Windows version 22). T-test and Chi-Square Test will be used for the comparison between groups. Correlation analysis will be based on the calculation of Pearson's rank correlation coefficients. Value of p below 0.05 will be considered as statistically significant. Consent to conduct the study was obtained from Local Ethic Committee of Inonu University.

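### Two operations are eligible, but neither allocation nor analysis takes account of which one was done: some precision is lost, and the estimate can shift if the arms happen to be imbalanced

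*Combined protocol and SAP*

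**What the plan says.** The population statement in the Study Protocol reads: "This study will perform in 60 adult patients who undergoing laparoscopic sleeve gastrectomy or gastric bypass surgery". The expected mix of the two operations is not given.

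On allocation, the Study Protocol says: "Randomly select patients will divide into two groups: Group L: low flow desflurane and group N: normal flow desflurane". It states no ratio, sequence method, blocking or stratification.

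Readings are tied to events, with no clock times. The first four are "before anesthesia (T₀), after intubation (T₁), before insufflation of CO₂ (T₂), after insufflation of CO₂ (T₃"), and the rest are "after reverse trendelenburg position (T₄), after supine position (T₅), after desufflation of CO₂ (T₆), after awakening from anesthesia (T₇"). Anesthesia and surgery times are also recorded. Type of operation is not in the list of recorded items.

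The Statistical Analysis section gives one sentence on the group comparison: "T-test and Chi-Square Test will be used for the comparison between groups". It names no covariate or stratum.

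**The concern.** T5, T6 and T7 follow the return to supine, desufflation and awakening. How long a patient has by then spent under CO2 insufflation, in reverse Trendelenburg and at the allocated flow depends on how long the operation took. If one operation tends to take longer than the other, it may be prognostic for the late cerebral saturation and hemodynamic readings, and for anesthesia and surgery times. Time at the allocated flow is also part of the exposure under study.

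Two things are at stake. First, any difference between operations stays in the error term and widens the comparison. Second, with about 30 patients per arm the operations can fall unevenly, and the estimated flow effect then carries part of the operation difference. As written, the plan would not prevent such an imbalance, adjust for it or report it.

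**Working it through.** **Inputs.** From the documents: 60 patients, two operations, two groups, unadjusted tests, significance at p below 0.05. Assumed, because the documents are silent: 30 per arm, two-sided testing, a bypass share q of 20%, 30% or 50%, and a difference d between operations of 0.3, 0.5 or 0.8 within-operation SD in a late reading.

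**The plan's own figure.** The total of 60 has no stated effect size, SD or power, so it cannot be reproduced. For scale, the standard error of a group difference is sqrt(2/30) = 0.258 SD, and 30 per arm detects (1.960 + 0.842) × 0.258 = 0.72 SD with 80% power.

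**Step 1: chance of imbalance.** With K bypass patients among 60 and 30 allocated to Group L, the number x of bypass patients in Group L is hypergeometric: P(x) = C(K, x) × C(60 − K, 30 − x) / C(60, 30). The gap between arms is |2x − K| / 30. For K = 18, a gap of at least 20 points means x ≤ 6 or x ≥ 12.

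| Bypass share | K | P(gap ≥ 10 points) | P(gap ≥ 20 points) |
|---|---|---|---|
| 20% | 12 | 33% | 10% |
| 30% | 18 | 40% | 16% |
| 50% | 30 | 44% | 20% |

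**Step 2: shift and lost precision.** A 20-point gap shifts the group difference by 0.20 × d, or 0.20 × d / 0.258 standard errors. The share of residual variance due to operation is d²q(1 − q) / [1 + d²q(1 − q)]. For d = 0.5 and q = 0.5 this is 0.0625 / 1.0625 = 5.9%.

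| d (SD) | Shift at 20 points | In standard errors | Variance share, q = 20% to 50% |
|---|---|---|---|
| 0.3 | 0.06 SD | 0.23 | 1.4% to 2.2% |
| 0.5 | 0.10 SD | 0.39 | 3.8% to 5.9% |
| 0.8 | 0.16 SD | 0.62 | 9.3% to 13.8% |

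**Step 3: error rate and power.** These come from 100,000 simulated trials per scenario with normal outcomes and 30 per arm, without stratified allocation. Ranges run over the three bypass shares.

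| d (SD) | Type I error of t-test, all trials | Type I error of t-test, gap ≥ 20 points | Power for 0.75 SD, t-test | Power for 0.75 SD, operation in model |
|---|---|---|---|---|
| 0.3 | 0.050 to 0.051 | 0.055 to 0.057 | 0.808 to 0.809 | 0.808 to 0.809 |
| 0.5 | 0.049 to 0.050 | 0.063 to 0.066 | 0.789 to 0.802 | 0.806 to 0.810 |
| 0.8 | 0.050 to 0.051 | 0.084 to 0.087 | 0.754 to 0.775 | 0.806 to 0.808 |

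With operation in the model, type I error is about 0.05 overall and 0.048 to 0.053 in the imbalanced trials, for d up to 1.0.

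**Step 4: half the fix.** If allocation is stratified but the unadjusted t-test is kept, its type I error falls to 0.035 to 0.049 for d of 0.3 to 0.8, and to 0.029 at d = 1.0 with an even mix. The test becomes conservative.

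**The case against.** A reader might infer that a chance imbalance makes the planned test invalid, or that it would simply pass for a flow effect. That does not follow. Random allocation already allows for chance imbalance in any covariate, and Step 3 shows the t-test holding its nominal level over all trials. Inflation appears only among trials that happen to be imbalanced, and at d of 0.3 to 0.5 it is slight.

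Nor do the documents support the wider reading that every intraoperative measurement is exposed. T1 follows intubation. T2 to T4 are tied to surgical set-up, but nothing in the plan suggests why the operation should alter them. The argument reaches T5 to T7.

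The inputs are also open to challenge. The documents give neither the mix of operations nor any difference between them in duration, saturation or pressure. Ventilation is adjusted to keep EtCO2 at 35 to 45 mmHg in everyone, which limits drift in that variable. Event-based readings compare patients at the same procedural stage, which is a reasonable choice. Age, ASA class and BMI are not stratified either, and the absence of stratification is read from a very brief allocation sentence.

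These objections stand as limits on size. They do not remove the point: operation helps define eligibility, bears on how long a patient is exposed before the late readings, and is used nowhere in the plan.

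**Conclusion.** The point holds as a modest matter of precision and of protection against an unlucky allocation. It is not a flaw in the validity of the test. Over the assumed range of operation differences (0.3 to 0.8 SD), ignoring operation leaves about 1% to 14% of residual variance in the error term. A gap of 20 points or more has a 10% to 20% chance and would shift the estimate by 0.06 to 0.16 SD at 20 points. At the low end the benefit is negligible. At 0.8 SD, which exceeds the flow effect that 30 per arm detects with 80% power, it is worth several points of power.

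All of this rests on the assumed mix, the assumed operation difference and 30 per arm. It is a low-priority improvement, worth making because it is cheap.

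**What to change.** Make the two changes together:

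1. **Allocation (Study Protocol).** Record the planned operation before allocation. State that patients are randomised 1:1 to Group L or Group N in permuted blocks of varying size, separately for sleeve gastrectomy and gastric bypass. This presumes that the planned operation is known by then, which the documents imply but do not say.
2. **Comparison (Statistical Analysis).** For continuous outcomes, replace the t-test with a linear model containing group and planned operation, ideally also the T0 value for variables measured at T0. For categorical outcomes such as complications, replace the plain chi-square test with a Cochran-Mantel-Haenszel test stratified by operation. Adjust for planned operation and not for recorded surgery time, which arises after allocation. Report the number of each operation by group.

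Stratifying while keeping the unadjusted t-test should be avoided, for the reason in Step 4. If allocation has already begun, leave it as it is, pre-specify the adjustment before the analysis and report operation by group.

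The cost is a second allocation list, one degree of freedom and a change of method for both types of outcome. No extra patients or procedures are needed. There is little gain if nearly all patients have the same operation.

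### The plan does not say when the arm is disclosed relative to the common 2 L/min phase, and no reading is tied to the flow change; opening the allocation when the existing MAC/BIS criterion is met would close most of the gap

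*Combined protocol and SAP*

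**What the plan says.** The combined protocol and SAP sets out the sequence in the Study Protocol section. Induction comes first. The next sentence reads "Randomly select patients will divide into two groups: Group L: low flow desflurane and group N: normal flow desflurane". Maintenance then begins "with a flow of 2 L/min in 0.5 O₂ oxygen-air mixture in both groups". The flows separate on a joint condition, "While target minimum alveolar concentration (MAC) was 1-1.5 and BIS values are 40-60 concurrently", at which point "the flow rate adjust to 0.75 L/min in Group L and 1.5 L/min in Group N".

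Readings are scheduled at T0 to T7. Each is attached to an anaesthetic or surgical event, for example "after intubation (T₁), before insufflation of CO₂ (T₂), after insufflation of CO₂ (T₃"; none is attached to the flow change.

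The Statistical Analysis section compares groups by t-test and chi-square test. Neither section states:

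- when the allocation is generated or disclosed, or whether it is concealed;
- who, if anyone, is blinded;
- how long the joint condition must hold, or by when it must be reached;
- whether the time of the flow change is recorded;
- which patients are analysed, or how a patient who never reaches the assigned flow is handled.

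**The concern.** The groups are described as existing during a phase in which they are treated alike. Whoever sets the flow has to know the arm at the switch, and nothing written prevents that person from knowing it sooner. During the common phase the anaesthetist titrates desflurane within a MAC range and decides when both conditions have been met. If the arm is known by then, depth of anaesthesia and time of switch can differ between groups for reasons other than flow. A difference in regional cerebral saturation (rSO2) produced in this way would be read as an effect of flow. Because the switch time need not be charted, it could not be traced afterwards.

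Two further consequences follow from where the flows separate. A patient who stays outside the joint range remains at 2 L/min, which is neither assigned flow. Keeping that patient in the comparison dilutes it, and dropping the patient departs from the randomisation. Also, no reading is guaranteed under the common maintenance anaesthetic just before separation. T0 is taken awake, T1 follows oxygen at 100% and intubation, and T2 may fall on either side of the switch.

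**Working it through.** **Sequence.** In the order of the text:

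| Step | What the text fixes | What it leaves open |
|---|---|---|
| Induction | Drugs given before the groups are mentioned | Whether the arm is already known |
| Division into L and N | Two groups | Method, ratio, concealment, time of disclosure |
| Common phase | 2 L/min, same gas mixture in both | Duration; whether the arm is known |
| Joint criterion | MAC 1-1.5 with BIS 40-60, same in both arms | Hold time, time limit, who judges it |
| Flow change | 0.75 or 1.5 L/min | Recording of its time; a reading just before it |

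So early knowledge of the arm is possible but not stated. No figure in the documents allows a bias from it to be calculated.

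**The plan's own figure.** The sample size is 60 ("This study will perform in 60 adult patients who undergoing laparoscopic sleeve gastrectomy or gastric bypass surgery"). It cannot be reproduced, because no effect size, standard deviation, power or dropout rate is given.

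**Dilution by patients who never switch (illustration).** Assume a share f of each arm stays at 2 L/min and is analysed as randomised. The mean difference is multiplied by (1 - f) and the information by (1 - f)².

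For power, assume 30 per arm, two-sided alpha 0.05 and the normal approximation. The difference detectable with 80% power is (1.960 + 0.842) × √(2/30) = 0.723 SD. With that as the true effect:

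- analysed as randomised, power = Φ[0.723 × (1 - f) × √(30/2) - 1.960];
- with non-switchers excluded, power = Φ[0.723 × √(30(1 - f)/2) - 1.960].

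| f (assumed) | Patients of 60 | 60 × (1 - f)² | Power, as randomised | Power, excluded |
|---|---|---|---|---|
| 0 | 0 | 60 | 80.0% | 80.0% |
| 2% | 1.2 | 57.6 | 78.4% | 79.2% |
| 5% | 3 | 54.2 | 75.9% | 78.0% |
| 10% | 6 | 48.6 | 71.3% | 75.7% |
| 20% | 12 | 38.4 | 61.1% | 70.7% |

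Exclusion looks better on power alone, but it selects on something that happens after randomisation and that knowledge of the arm may influence.

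**Value of a reading just before the switch (illustration).** With a baseline covariate that correlates r with the later reading, residual variance is (1 - r²) of the raw variance: 1 - 0.6² = 0.64 and 1 - 0.8² = 0.36. Both correlations are assumed. The lower one stands for the awake reading, the higher one for a reading under the same anaesthetic. The planned t-test uses no covariate, so it would realise neither gain.

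**The case against.** The case on the other side has several parts, and much of it stands.

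- **Sentence order is not a time stamp.** A reader might infer that the anaesthetist knows the arm during the common phase. The documents do not say so. Describing a phase as applying to both groups shows how the text is organised, not when an envelope is opened. What stands is that disclosure and concealment are unspecified.
- **The trigger is not left to the team.** It is a numerical criterion read from monitors and common to both arms. Discretion is confined to titration and to how promptly, and after how long, the condition is judged met.
- **Propofol.** A reader might add induction dosing to the choices that knowledge of the arm could influence. Induction is described before the groups are formed, so the point holds only if the arm is known earlier still. The desflurane and switch-time points do not need that assumption.
- **Patients who never switch are hypothetical.** Both conditions are titration targets and no hold time is required, so one concurrent moment would satisfy the text. One reading out of range does not make a patient a non-switcher. Their share may be close to zero.
- **Lighter remedies exist.** Stating the concealment and disclosure time, charting the switch time and analysing as randomised would cover much of the concern. A reading before the switch can be added without moving randomisation.

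None of this supplies the missing statements. The lighter remedies also leave in the trial any patient who never receives an assigned flow.

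**Conclusion.** The point holds in a limited form. As written, the plan permits the arm to be known while desflurane is titrated and the joint criterion is judged. It gives no means of detecting a difference in switch time, and it has no rule for a randomised patient who stays at 2 L/min. It does not show that any of these will happen.

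The size of a timing or depth bias cannot be derived from the documents. Loss of information through non-switchers runs from negligible (about 2 points of power at f = 2%) to serious (about 19 points at f = 20%). This rests on an assumed f equal in both arms, an assumed 30 per arm and an assumed effect of 0.723 SD. Dilution is therefore the secondary argument; undisclosed timing and the lack of concealment are the main ones.

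It would also be too strong to conclude that moving the disclosure solves everything. The anaesthetist still titrates with the arm known after the switch, and readings tied to surgical events can still precede a late switch. The precision gain from a new baseline appears only if the analysis adjusts for it. No view is taken on the flow rates or on the MAC/BIS criterion itself.

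**What to change.** In the Study Protocol section:

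1. Keep the allocation sealed through induction and the common 2 L/min phase.
2. When the protocol's existing criterion is met, chart one full set of readings and the clock time.
3. Only then open the allocation and set the assigned flow.
4. List patients who never meet the criterion as not randomised in the flow chart, and continue until 60 have been randomised.

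In the Statistical Analysis section: analyse every randomised patient in the assigned group, and compare later rSO2 readings by ANCOVA with the reading taken just before opening as covariate, in place of the unadjusted t-test.

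The cost is a change of wording, one extra charted set of readings on monitors already attached, and opening the allocation in theatre. A few more patients may need to be consented: 60/(1 - f) is about 61 at f = 2%, 67 at 10% and 75 at 20%. The conclusion is then limited to patients who meet the criterion, and the report should say so. The charted switch time also shows which scheduled readings preceded the flow change, although it does not prevent that.

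### The between-group comparison names no reading time and states no role for the pre-anaesthesia value, so it gives up precision and leaves the test of the flow effect open until the data are seen

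*Combined protocol and SAP*

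**What the plan says.** In the Study Protocol, allocation is random ("Randomly select patients will divide into two groups"), but the arms are treated alike at first: "Initially, anesthesia maintain with desflurane inhalation with a flow of 2 L/min in 0.5 O₂ oxygen-air mixture in both groups". The flows part on a condition met by each patient individually, "While target minimum alveolar concentration (MAC) was 1-1.5 and BIS values are 40-60 concurrently", at which point "the flow rate adjust to 0.75 L/min in Group L and 1.5 L/min in Group N".

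The recorded variables begin "HR, SpO₂, EtCO₂, mean arterial pressure (MAP), BIS values, left regional cerebral oxygen saturations (LrSO₂" and include the right-sided saturation. The eight reading times are set by anaesthetic, surgical or positioning events. They start before anaesthesia (T0) and after intubation (T1), continue "before insufflation of CO₂ (T₂), after insufflation of CO₂ (T₃", and end "after reverse trendelenburg position (T₄), after supine position (T₅), after desufflation of CO₂ (T₆), after awakening from anesthesia (T₇". None is defined by the flow change. The remaining recorded items are covered by "Also anesthesia and surgery times, perioperative and postoperative complications will record"; the time of the flow change is not listed.

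The Statistical Analysis section compares groups by t-test and chi-square test, adds a correlation analysis, and sets significance at p below 0.05. It names no primary outcome, reading time, covariate, change score or repeated-measures model, and it does not mention T0. The sample size is 60, without a derivation.

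**The concern.** Three things follow from an unadjusted test at an unnamed time.

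- **Precision.** T0 is measured before any difference in treatment, so it is a proper baseline covariate. Leaving it out of the comparison keeps between-patient variation in the error term that could be removed at no cost, which matters in a trial of 60.
- **Choice of reading.** Seven post-baseline readings are available. If none is named, the one reported as the test of the flow effect can be picked after the results are known, and a nominal 0.05 no longer describes the chance of a false positive.
- **Meaning of a reading.** The readings do not all bear on the flow contrast. T0 precedes it, T1 probably does, T2 cannot be placed from the documents, T3–T6 are probably under assigned flow, and T7 follows awakening. A null result at T2 could mean that flow has no effect or that flow did not yet differ.

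**Working it through.** **Inputs from the documents.** 60 patients; two randomised groups; significance at 0.05; eight readings, T0 to T7.

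**Assumptions, because the documents are silent.** 30 per arm; two-sided testing; SD of 1 at every reading; all correlations; an effect of d = 0.736 SD, chosen because it gives 80% power for one unadjusted reading. The plan states no effect size, SD or power, so there is no planned figure to reproduce.

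**Step 1. One reading, unadjusted.** Noncentrality = d / √(1/30 + 1/30) = 0.736 / 0.2582 = 2.85, with 58 df. Power = 80%.

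**Step 2. One reading, adjusted for T0.** The residual variance is 1 − r², where r is the correlation between T0 and the later reading. Noncentrality = 0.736 / √[(1 − r²) × 2/30], with 57 df.

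| r | 1 − r² | Noncentrality | Power | Difference detectable at 80% power |
|---|---|---|---|---|
| none used | 1 | 2.85 | 80% | 0.74 SD |
| 0.3 | 0.91 | 2.99 | 84% | 0.70 SD |
| 0.4 | 0.84 | 3.11 | 86% | 0.67 SD |
| 0.5 | 0.75 | 3.29 | 90% | 0.64 SD |
| 0.7 | 0.51 | 3.99 | 98% | 0.52–0.53 SD |

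The allocation ratio is not stated. With a 20/40 split, the same effect gives 75% unadjusted and 79%, 82%, 86% and 96% adjusted, so the gain does not depend on equal arms.

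**Step 3. Unnamed time.** If all seven post-baseline readings of one saturation measure were tested at 0.05 with no true effect, the chance of at least one false positive would be 1 − 0.95⁷ = 30% if the readings were independent. With 30 per arm, simulation gives about 23% if every pair of readings correlates 0.5 and about 18% at 0.7. Testing left and right sides separately would add to this.

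**Step 4. What naming a summary gains and risks.** Take the T3–T6 mean adjusted for T0, with correlation w within T3–T6 and b with T0. The variance of the mean is (1 + 3w)/4 and its covariance with T0 is b, so the residual variance is (1 + 3w)/4 − b².

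- Pattern A (w = b = 0.5): 0.625 − 0.25 = 0.375.
- Pattern B (w = 0.7, b = 0.4): 0.775 − 0.16 = 0.615.

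A constant effect enters the mean as d, and an effect at only one of the four readings enters as d/4 = 0.184. For four separate T0-adjusted tests, each is run at 0.05/4 = 0.0125.

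| Scenario (0.74 SD effect) | Pattern A | Pattern B |
|---|---|---|
| Constant effect, adjusted mean | 99.6% | 95% |
| Effect at one reading only, adjusted mean | 21% | 15% |
| Effect at one reading only, adjusted test of that reading at 0.0125 | 76% | 70% |
| Effect at one reading only, adjusted test of that reading named in advance at 0.05 | 90% | 86% |

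The last two rows are the like-for-like comparison, since both use T0. Spreading alpha over four times costs 14 points (90 − 76) or 16 points (86 − 70) relative to naming the right reading in advance.

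**The case against.** The strongest reply is that nothing here invalidates the trial. Allocation is random, so an unadjusted comparison by assigned group is valid at any reading. The documents also do not rule out a t-test on change from T0, since no variable or time is specified. Every correlation above is assumed, and at 0.3 the gain from adjustment is only four points. All of this stands. The accurate statement is that no role for T0 is stated, not that T0 will go unused, and the loss is one of precision and pre-specification, not of bias from omitting a covariate.

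A reader might go further and infer that late switching dilutes the effect substantially, so that the trial loses much of its power because the switch time is not listed as recorded. The documents do not support that. They do not say how long the trigger takes, and the share not yet switched at T3 may be zero. To weaken a T3–T6 mean in proportion to the unswitched share, those patients would have to remain unswitched through T6, after desufflation, and nothing in the protocol suggests this. If a share f were unswitched at T3 alone, the mean would lose only f/4 of the effect. Nor would logging the switch time add power, because readings should not be selected on it.

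There is also partial evidence on the trigger in the planned data: BIS is recorded at each time, and the protocol says age-related MAC values will be determined. Neither gives the time of the change, so a note of it remains useful for interpretation, but only as a reporting aid.

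**Conclusion.** The point holds as a matter of precision and pre-specification. The stated between-group analysis names no time and gives T0 no stated role. Adjusting one reading for T0 would raise power from 80% to between 84% and 98% over assumed correlations of 0.3 to 0.7 (30 per arm, two-sided 0.05, 0.74 SD effect). Leaving the time open allows a data-driven choice among seven readings, of which T1 probably, and T2 possibly, precede any flow difference, and T7 follows awakening. The case does not depend on slow switching: it stands even if every patient reaches the assigned flow before T2. It should be corrected before analysis. It does not make the unadjusted test invalid, and the size of the gain depends on correlations that the documents do not give.

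**What to change.** 1. **Analysis.** Compare cerebral saturation between groups by ANCOVA with the T0 value as covariate, or by a mixed model with group, time and T0 if readings are missing. Include all randomised patients by assigned group, including any whose flow was never changed. Analyse left and right as recorded, or say in advance how they will be combined.
2. **Tested reading.** Name in advance the reading or summary that tests the flow effect. One reasonable option is the T3–T6 mean, with T0 as baseline only, T1–T2 descriptive, T7 as recovery, and T0-adjusted estimates with confidence intervals at each time alongside. If an effect is expected in one phase only, name that reading, or test the four times at 0.0125 each.
3. **Reporting aid.** Note the time of the flow change (or that it never occurred), and report how many patients per group were on assigned flow at T2 and at T3. Do not use this to choose or exclude readings, because that would be selection after randomisation.

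**Cost.** A short paragraph of analysis wording and one time entry per patient, with no extra patients or saturation readings. The trade-off lies in item 2. The T3–T6 mean is strong for a sustained effect but has only 21% or 15% power for one confined to a single reading. The four-test option protects against that, at the price shown in the working. The investigators should choose by where they expect the effect, before seeing the data.

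### T0 rSO₂ is recorded in every patient before the flows differ but has no stated use; ANCOVA on T0 would be more precise than the planned t-test at almost no cost

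*Combined protocol and SAP*

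**What the plan says.** The Statistical Analysis section gives one sentence to between-group comparisons: "T-test and Chi-Square Test will be used for the comparison between groups". It names no covariate, change score or repeated-measures model. The only other analysis is a correlation ("Correlation analysis will be based on the calculation of Pearson's rank correlation coefficients"), with no variables named and no role for a baseline value.

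The Study Protocol section has cerebral oximetry in all patients. Left and right rSO₂, with HR, SpO₂, EtCO₂, MAP and BIS, "will record at before anesthesia (T₀), after intubation (T₁") and at six further points up to T7.

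On the intervention, the same section says: "Initially, anesthesia maintain with desflurane inhalation with a flow of 2 L/min in 0.5 O₂ oxygen-air mixture in both groups". The groups part only when the MAC and BIS targets have been met, at which stage "the flow rate adjust to 0.75 L/min in Group L and 1.5 L/min in Group N".

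The trial size is given without a derivation: "This study will perform in 60 adult patients".

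**The concern.** T0 is taken before anaesthesia, both groups then start at the same flow, and the flows separate later still. T0 rSO₂ therefore cannot be affected by the allocated flow, which makes it a legitimate covariate. It is also the same quantity as the outcome, measured in the same patient, so it is a natural candidate to predict later values.

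Two things follow from leaving its use unstated.

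- **Precision.** In an unadjusted t-test, the part of between-patient variation that T0 could explain stays in the error term. A fraction rho of any chance T0 difference between the arms also carries into the estimated effect.
- **An open choice.** A t-test on raw values and a t-test on change from T0 both fit the text. Their power differs, and which is better depends on whether rho is below or above 0.5. If the choice is made after the data are seen, the result can influence it.

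**Working it through.** The plan states no power, effect size or SD, so there is no figure to reproduce.

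**Inputs from the documents:** N = 60; two groups; significance at p below 0.05.

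**Assumptions, not in the documents:** 30 per arm; two-sided test; no dropout; equal SDs at T0 and later; true difference 0.5 SD; rho of 0, 0.3, 0.5 and 0.7.

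**Raw t-test.** SE = √(2/30) = 0.258 SD. Noncentrality = 0.5/0.258 = 1.94 on 58 df, giving power 47.8%. The difference detectable with 80% power is 0.736 SD.

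**Change-score t-test.** Variance relative to raw = 2(1 − rho), which is 1.4, 1.0 and 0.6 at rho 0.3, 0.5 and 0.7. It beats the raw t-test only when rho exceeds 0.5.

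**ANCOVA on T0.** Residual variance is multiplied by (1 − rho²). Estimating one covariate costs a factor (N − 3)/(N − 4) = 57/56 = 1.018, and the test has 57 df. The equivalent N is 60 divided by the net variance ratio.

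| rho | 1 − rho² | Net variance ratio | Equivalent unadjusted N | Power, raw | Power, change | Power, ANCOVA | Detectable at 80%, ANCOVA |
|---|---|---|---|---|---|---|---|
| 0 | 1.00 | 1.018 | 59 | 47.8% | 27% (simulated) | 47.1% | 0.742 SD |
| 0.3 | 0.91 | 0.926 | 65 | 47.8% | 36.3% | 50.7% | 0.708 SD |
| 0.5 | 0.75 | 0.763 | 79 | 47.8% | 47.8% | 58.7% | 0.643 SD |
| 0.7 | 0.51 | 0.519 | 116 | 47.8% | 69.1% | 75.2% | 0.530 SD |

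**Break-even.** (1 − rho²)(57/56) = 1 gives rho² = 1/57, so rho = 0.13. Below that, ANCOVA is very slightly worse than the raw t-test.

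**Simulation check.** With 10,000 trials per setting, ANCOVA power at 0.5 SD was 46.9%, 50.8%, 59.4% and 75.0% for rho 0, 0.3, 0.5 and 0.7. Its type I error was between 4.6% and 5.4%.

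**Chance imbalance.** The expected absolute T0 difference between arms is 0.258 × √(2/π) = 0.206 SD. Multiplied by rho, this shifts the unadjusted estimate by 0.06, 0.10 and 0.14 SD at rho 0.3, 0.5 and 0.7.

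**Unequal arms.** The allocation ratio is not stated. With a 20:40 split, power is 43.5% for the raw t-test and 46.2%, 53.8% and 70.2% for ANCOVA, so the pattern does not depend on equal arms.

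**The case against.** The strongest reply is that nothing here is an error. An unadjusted t-test in a randomised trial is unbiased and holds its 5% type I error. Chance imbalance does not overturn that: at the expected T0 imbalance, the conditional error of the raw test is 4.2%, 3.5% and 2.2% at rho 0.3, 0.5 and 0.7, all below 5%. This stands, and the point is about efficiency only.

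The second reply is that rho is unknown and may be modest. T0 is an awake reading; most later readings follow induction and 0.5 O₂, some of them also CO₂ insufflation and changes of position. At rho 0.2, ANCOVA gives 48.6% power against 47.8%. If the true difference is 0.736 SD, rho 0.3 lifts power only from 80.0% to 82.9%. This stands as a limit on the size of the gain. It does not change the direction of the advice, because the most that can be lost is 0.7 percentage points at 0.5 SD (47.8% to 47.1%), against 11 gained at rho 0.5 and 27 at rho 0.7.

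Third, the plan names no primary rSO₂ side or time point, and a covariate cannot repair an undefined comparison. That is true, so the change below is conditional on naming them.

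Fourth, the plan never mentions a change score, and raw values may be the plain reading. That is fair: the change-score figures show what the silence permits, not a loss the plan is known to incur.

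**Conclusion.** The point holds. A baseline measurement that is already collected, and that the allocated flow cannot affect, is given no use. ANCOVA on it is at least as powerful as either form of t-test across rho 0.3 to 0.7. Net of its own cost, it reduces variance by about 7%, 24% and 48% at rho 0.3, 0.5 and 0.7, so the gain is small at the low end and material from about 0.5 upward. If T0 does not predict later rSO₂, the cost is about 2% in variance.

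These sizes rest on assumed values for rho, the allocation ratio and sidedness; the power figures also rest on the assumed 0.5 SD difference. The t-test remains valid, so this is a recommended improvement and not a correction of bias. It is worth making because the sample is fixed at 60 with no stated justification, and adjustment adds precision without adding patients.

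**What to change.** In the Statistical Analysis section, state how T0 is used.

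- First name the rSO₂ outcome (left, right or their average) and the time point or points, all after the flows have separated. The protocol does not tie the flow change to a numbered time point, so this needs to be made explicit.
- Replace the t-test for rSO₂ with ANCOVA, with group as the factor and T0 rSO₂ as covariate. If several time points are analysed together, use a mixed model with the same covariate.
- Use the same-side T0 value if the sides are analysed separately, or the mean T0 value if they are averaged.
- Treat MAP and HR in the same way with their own T0 values. The calculation above is in SD units, so the gain for each depends on its own rho.
- Show T0 values by group descriptively.

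The cost is one or two sentences once the outcome and time points are settled, and one degree of freedom in the analysis. No new data and no change to conduct are needed.
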